Study Protocol

Title: Effects of Topical Bromfenac Solution on Macular Thickness in Cataract Patients Undergoing Phacoemulsification Surgery

Clinical Trial Registration Number: NCT06785090

Document Date: March 28, 2025.

1. Background and Rationale

Cystoid macular edema (CME) is a common postoperative complication following cataract surgery. Bromfenac, a topical nonsteroidal anti-inflammatory drug (NSAID), is hypothesized to reduce macular thickness and prevent CME. This study investigates the efficacy and safety of bromfenac in patients undergoing phacoemulsification.

2. Study Objectives

- **Primary Objective:** To assess the effect of bromfenac 0.09% ophthalmic solution on macular thickness after phacoemulsification.
- **Secondary Objective:** To evaluate potential adverse effects, including corneal erosion.

3. Study Design

- **Study Type:** Randomized controlled trial
- **Allocation:** Randomized
- **Intervention Model:** Parallel assignment
- **Masking:** Single-blinded (Investigator)

4. Eligibility Criteria

Inclusion Criteria:

1. All patients 18 years of age and older.
2. Patients diagnosed with cataracts.

Exclusion Criteria

- 1- Patients less than 18 years of age.
- 2- Patients with glaucoma, ocular hypertension, pseudo-exfoliation syndrome, or any optic nerve disease.
- 3- Patients with ocular diseases that might influence macular thickness, such as age-related macular degeneration, epiretinal membrane, history of uveitis, intraoperative complications, and traumatic cases.
- 4- Patients have undergone previous ocular surgery in the same eye, such as vitrectomy, intravitreal injection, retinal laser therapy, or corneal surgery
- 5- Patients who developed severe adverse effects from other drugs or had complications intraoperatively or postoperatively unrelated to bromfenac.
- 6- Patients take antiglaucoma medications.

- 7- Patients lost to follow-up.
- 8- Patients with an allergy to one of the postoperative medications.

5. Intervention and Follow-up

- **Group one-** consisted of forty-five patients who received 0.09% bromfenac ophthalmic solution twice daily in addition to Moxifloxacin 0.5% ophthalmic drops every 6hrs and Dexamethasone phosphate 0.1% ophthalmic drops every 4-6hrs.
- **Group two-** consisted of forty-two patients who received only Moxifloxacin 0.5% every 6hrs and Dexamethasone phosphate 0.1% ophthalmic drops every 4-6hrs without the administration of bromfenac 0.09% ophthalmic drops.

6. Outcome Measures

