- **Primary Outcome:** Change in central macular thickness (CMT) measured by Optical Coherence Tomography (OCT)
- **Secondary Outcomes:** adverse effects

7. Statistical Methods

- Sample size calculation based on a power of 80% and significance level of 0.05.
- Independent t-test for intergroup comparisons.
- Paired t-test for intragroup pre- and post-treatment comparisons.

Statistical Analysis Plan (SAP)

1. Introduction

This SAP outlines the statistical methodologies for analyzing data collected in the clinical trial titled "Effects of Topical Bromfenac Solution on Macular Thickness in Cataract Patients Undergoing Phacoemulsification Surgery."

2. Study Population

- **Intent-to-Treat (ITT) Population:** All randomized patients.
- **Per-Protocol (PP) Population:** Patients who adhered to treatment and completed follow-up assessments.

3. Statistical Methods

- **Descriptive Analysis:** Means and standard deviations (SD) for continuous variables.
- **Inferential Analysis:**

- **Primary Outcome:** Two-sample t-test for between-group comparisons of CMT change.
- **Secondary Outcomes:**
 - Incidence of CME: Chi-square test.
 - Adverse effects: Fisher's exact test.

4. Handling of Missing Data

- **Missing data <5%:** Complete case analysis.
- **Missing data >5%:** Multiple imputation methods.

5. Software Used

All analyses will be performed using SPSS.

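### The primary t-test on CMT change is valid but leaves baseline CMT unused as a covariate; ANCOVA would usually be more precise at almost no cost

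*Combined protocol and SAP*

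**What the plan says.** SAP section 3 gives the primary analysis as "Two-sample t-test for between-group comparisons of CMT change". Protocol section 7 agrees: "Independent t-test for intergroup comparisons". Neither document names a covariate or an adjusted model.

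A preoperative CMT must be available. Protocol section 6 defines the primary outcome as a change on OCT, and protocol section 7 also plans a "Paired t-test for intragroup pre- and post-treatment comparisons". Collection of baseline is therefore implied, although no OCT schedule is given and no postoperative visit is named for the primary outcome.

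On sample size, protocol section 7 says only "Sample size calculation based on a power of 80% and significance level of 0.05". Protocol section 5 gives 45 patients on bromfenac and 42 controls.

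**The concern.** Baseline CMT enters the primary comparison only by subtraction. That is the best use of it only if the true slope of postoperative on baseline CMT is 1. This slope equals the pre/post correlation times the ratio of postoperative to baseline SD. Below 1, the change score over-corrects for baseline; above 1, it under-corrects. In both cases the change contrast stays correlated with any chance baseline difference between the groups, and its variance is larger than it need be. ANCOVA estimates the slope from the data.

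The stake is precision, not bias or type I error. With 87 patients precision is limited, and the covariate needs no new measurement.

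**Working it through.** **Inputs from the documents.** Group sizes are 45 and 42 (protocol section 5). Power is 80% and significance level 0.05 (protocol section 7); I take the test as two-sided, which is not stated.

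**Inputs assumed.** The effect size, SD of change, pre/post correlation ρ and SD ratio k = postoperative SD / baseline SD are not given. I use ρ from 0.5 to 0.9 and k from 1.0 to 1.5, with baseline SD set to 1.

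**Step 1: the plan's own figure.** The 80% cannot be reproduced without a difference and an SD, so I solved backwards. √(1/45 + 1/42) = 0.2146. With 85 df, 80% power needs a noncentrality of 2.834. The difference is therefore 2.834 × 0.2146 = 0.608 SD of change. All powers below are at this effect.

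**Step 2: variances.**

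- Change score: 1 + k² − 2ρk.
- ANCOVA: k²(1 − ρ²) × 84/83. The factor 84/83 is the expected cost of estimating the slope with N = 87, that is 1 + 1/(N − 4).
- Residual df fall from 85 to 84, which moves the critical t from 1.9883 to 1.9886.

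Example with k = 1, ρ = 0.5: the change-score variance is 1 + 1 − 1 = 1 and the ANCOVA variance is 0.75 × 84/83 = 0.759. The noncentrality becomes 2.834/√0.759 = 3.25, and power is 89.5%.

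**Step 3: ANCOVA power where the t-test has 80%.**

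| SD ratio k | ρ = 0.5 | ρ = 0.7 | ρ = 0.8 | ρ = 0.9 |
|---|---|---|---|---|
| 1.0 | 89.5% | 85.5% | 83.5% | 81.5% |
| 1.1 | 86.9% | 82.7% | 80.8% | 79.5% |
| 1.25 | 83.8% | 80.3% | 79.5% | 81.5% |
| 1.5 | 80.9% | 79.6% | 81.4% | 88.5% |

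In the k = 1 row the variance ratios are 0.759, 0.860, 0.911 and 0.961, so the 95% CI is about 13%, 7%, 5% and 2% narrower. The table leaves out ratios below 1, where the gain is larger: at k = 0.8, power runs from 93.6% to 95.8%.

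**Step 4: worst case and break-even.** If the slope is exactly 1 (for example k = 1.25, ρ = 0.8), the variance rises by 84/83 − 1 = 1.2% and power is 79.5%. ANCOVA has the smaller expected variance when (1 − R²) × 84/83 < 1, where R² is the share of within-group variance in change explained by baseline. That requires R² > 1/84 = 0.0119, or an absolute correlation above 0.109.

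**Step 5: chance baseline imbalance.** A one-standard-error baseline difference is 0.2146 baseline SD. It moves the expected change contrast by (slope − 1) × 0.2146, which in absolute size is 0.107, 0.064, 0.027 and 0 baseline SD at slopes 0.5, 0.7, 0.875 and 1. The t-test's standard error allows for this on average, so it is the same efficiency loss seen conditionally and not an additional harm.

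**Step 6: simulation check.** With 40,000 trials in each of nine settings, type I error was 4.9–5.2% for the t-test and 4.8–5.2% for ANCOVA. Simulated ANCOVA power for ρ = 0.5, 0.7, 0.8 and 0.9 was 89.7, 85.4, 83.6 and 81.6% at k = 1, and 83.8, 80.4, 79.2 and 81.4% at k = 1.25, in line with the table.

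**The case against.** The strongest reply is that nothing is broken. The t-test is prespecified, the two documents agree on it, and the whole benefit rests on values they do not give. In the table, 9 of 16 cells change power by only −0.5 to +1.5 points, three of them are small losses, and only four gain 5 points or more. A low-gain case is also plausible here. If surgery adds thickness roughly independently of baseline, the slope is near 1 and the postoperative SD exceeds the baseline SD. For slopes of 0.9 to 1.0 and SD ratios of 1.1 to 1.5, ANCOVA power is about 79.5–80.5%.

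That stands as a limit on the size of the benefit. It does not reverse the recommendation: the loss never exceeds 0.5 points, the gain within the table reaches 9.5, and the documents give no reason to assume a slope of 1.

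The second reply is that protocol section 5 uses the past tense ("consisted of forty-five patients who received 0.09% bromfenac ophthalmic solution"), so outcome data may already exist and a change of primary analysis may come too late. This stands, and the fix is conditional for that reason.

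Third, calling the t-test valid refers only to the choice of test. Exclusion criteria 5 and 7 in protocol section 4 (complications, loss to follow-up) remove patients after randomisation, and 45 and 42 may be analysed rather than randomised numbers. That is a separate problem, and ANCOVA does not repair it.

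**Conclusion.** The concern holds as a worthwhile improvement to a valid analysis. Over the range examined (ρ 0.5–0.9, k 1.0–1.5), replacing the t-test by ANCOVA changes power by between −0.5 and +9.5 points from 80%. The gain is clearest when the SDs are similar and the correlation is moderate; it disappears when the slope is close to 1. Where this trial lies in that range cannot be determined from the documents. The figures assume a two-sided 0.05 test, 45 and 42 analysed patients, a linear relation with a common slope in both groups, and normally distributed data.

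**What to change.** In SAP section 3, make the primary analysis an ANCOVA of postoperative CMT on treatment group and baseline CMT. Using change as the dependent variable gives the same treatment estimate. Report the adjusted mean difference with its 95% CI, and name the single postoperative visit it refers to. Keep the unadjusted t-test on change as a sensitivity analysis, and amend protocol section 7 to match.

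Make this the primary analysis only if it is written and dated before anyone has seen unblinded outcome data. If outcomes have been seen, switching would add analytic flexibility: leave the t-test primary and report ANCOVA as a labelled sensitivity analysis.

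The cost is a short SAP edit and one protocol line. No new data are needed and SPSS, the software named in SAP section 5, fits the model. The statistical cost is one degree of freedom plus the estimation of the slope: at worst about 1.2% more variance, or 0.5 power points.

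### Does a chi-square test for CME incidence break down with only 45 and 42 patients?

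*Combined protocol and SAP*

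**What the plan says.** SAP section 3 lists two secondary analyses of event counts: "Incidence of CME: Chi-square test" and "Adverse effects: Fisher's exact test". It states no rule for small expected counts, no fallback to an exact test, and no choice between corrected and uncorrected chi-square.

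The group sizes come from protocol section 5. The bromfenac group "consisted of forty-five patients who received 0.09% bromfenac ophthalmic solution twice daily" and the control group "consisted of forty-two patients who received only Moxifloxacin 0.5% every 6hrs". The SAP's intention-to-treat population is "All randomized patients", so 45 and 42 are the natural denominators.

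The only hint of how often CME will occur is qualitative, in protocol section 1: "Cystoid macular edema (CME) is a common postoperative complication following cataract surgery". Protocol section 6 gives "Secondary Outcomes: adverse effects" and does not name CME, so the SAP line is the only place where its analysis is specified.

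**The concern.** Chi-square is a large-sample test, and the usual advice is to avoid it when an expected count is below 5. Here that happens whenever 10 or fewer CME cases occur in the two groups together, which is likely unless CME is frequent. The SAP uses Fisher's exact test for the neighbouring outcome in the same patients, so the different choice for CME looks like an oversight.

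There are also concrete tables in which the two tests fall on opposite sides of 0.05. Preventing CME is part of the trial's rationale, so a CME p-value just below 0.05 could be cited as clinical support. If that p-value came from a test with an inflated error rate, the claim would be unsound.

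**Working it through.** **Inputs.** Groups of 45 and 42 (protocol section 5). Significance level 0.05 (protocol section 7), taken as two-sided because the sidedness is not stated. CME rate: not given, so a range is assumed. The plan has no figure of its own to reproduce on this point. The 80% power in protocol section 7 comes without an effect size and is not tied to CME.

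**Step 1: the threshold.** With m CME cases in total, the smallest expected count is 42 × m / 87. For m = 10 this is 4.83; for m = 11 it is 5.31. So 11 cases are needed (11/87 = 12.6%). The chance of 10 or fewer is 99.6% at a common rate of 5%, 75% at 10%, 23% at 15% and 2.7% at 20%. The premise of the concern is correct.

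**Step 2: tables where the tests disagree.** With 0/45 versus 4/42, uncorrected chi-square is 87 × (45 × 4)² / (45 × 42 × 4 × 83) = 4.49, p = 0.034. Fisher's p is C(42,4)/C(87,4) = 111,930/2,225,895 = 0.0503. With 4/45 versus 0/42, chi-square is 87 × (4 × 42)² / (45 × 42 × 4 × 83) = 3.91, p = 0.048; Fisher's p is (148,995 + 111,930)/2,225,895 = 0.117. Up to 10 cases, three more tables disagree (bromfenac versus control cases): 1 vs 6 (0.039 against 0.053), 5 vs 0 (0.026 against 0.056) and 7 vs 1 (0.034 against 0.059).

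Disagreement alone does not show which test is at fault. That needs the true error rates.

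**Step 3: true false-positive rate.** For a common rate p, add Binomial(45, p) × Binomial(42, p) over every table that the test rejects at 0.05:

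| Assumed common CME rate | Chi-square, uncorrected | Chi-square, continuity-corrected | Fisher's exact |
|---|---|---|---|
| 2% | 0.9% | 0.02% | 0.07% |
| 5% | 4.3% | 0.5% | 1.0% |
| 10% | 4.9% | 1.7% | 2.6% |
| 15% | 5.2% | 2.2% | 3.3% |
| 20% | 5.1% | 2.6% | 3.6% |

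For rates up to 12.6%, where sparse counts are the usual case, the maximum for uncorrected chi-square is 5.06%. It reaches 5.3% only near a rate of 50%, where expected counts are large.

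At a 5% rate, the sparse tables that chi-square rejects and Fisher does not have total probability 3.3%. That is essentially the whole gap between 4.3% and 1.0%. Those tables are part of the 5% allowance that Fisher's test leaves unused.

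**Step 4: error rate given the number of cases.** Conditional on the total, uncorrected chi-square falsely rejects as follows:

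| Total cases | 1–3 | 4 | 5 | 6 | 7 | 8 | 9 | 10 |
|---|---|---|---|---|---|---|---|---|
| False rejection | 0% | 11.7% | 5.6% | 2.7% | 5.3% | 5.9% | 3.1% | 4.5% |

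Only the total of 4 stands out. Exactly 4 cases has probability C(87,4) × 0.05⁴ × 0.95⁸³ = 19.7% at a 5% rate, 3.5% at 10% and 0.16% at 15%. Even at 5%, the totals of 1 to 3, which never reject, keep the overall figure at 4.3%.

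Nor does an expected count of 5 mark where trouble starts. At 13 cases, with every expected count above 5, the table 10 vs 3 still has chi-square p = 0.049 and Fisher p = 0.071.

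**Step 5: cost of switching.** For true rates of 2% on bromfenac and 10% on control, power is 34.7% with uncorrected chi-square and 22.0% with Fisher's test. The loss is (34.7 − 22.0)/34.7 = 37% of what there was.

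**The case for a change.** The best counter-argument is conditional. Once exactly 4 cases have been seen, a reader may care about the error rate for 4 cases, and 11.7% is more than double the nominal level. That reading is legitimate, and it is the view from which Fisher's test is derived. But the design does not fix the number of CME cases, so averaging over it is an equally sound basis for judging a pre-specified test. On that basis the level holds. Quoting the total of 4 alone also leaves out the totals on either side, which lie between 0% and 5.9%.

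A second argument is that the SAP does not name one version of the test. With 0 versus 4 cases, uncorrected chi-square gives 0.034 and the corrected version 0.108. This stands as missing detail. It does not show a wrong result, because neither version materially exceeds 5% at any of the rates tried.

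Third, two event outcomes in the same patients get different tests without explanation, and CME is absent from protocol section 6. Both observations are true. The first is not a contradiction, since either test keeps its level here. The second is a matter of aligning protocol and SAP and has no bearing on whether chi-square is valid.

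**Conclusion.** The concern does not hold. The expected-count convention would probably be broken if CME is at or below about 10%, but with 45 and 42 patients this does no material harm: the true false-positive rate of uncorrected chi-square is at most 5.06% for any common rate up to 12.6%. The disagreements with Fisher's test mostly reflect that test's conservatism. Choosing between the two is a trade-off on which reasonable statisticians differ, and switching would lower power from 35% to 22% in the 2% versus 10% example.

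This rests on two-sided testing at 0.05, denominators of 45 and 42, and assumed CME rates, since the documents give none. Stating the version of the test, adding an interval for the risk difference and listing CME in protocol section 6 would be tidier. None of these would correct a wrong result, and the outcome is secondary.
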